8.2 Exclusion Criteria

Patients meeting any of the following criteria will be excluded from study participation:

- Women who are pregnant, breast feeding or of child bearing potential and not using contraception
- Absence of a qualifying type of cancer as defined by standard ICD-10 diagnostic criteria
- Patient receiving only radiation therapy
- Patient with an ECOG performance status of 2 or higher

- Patient with an expected cancer survival of less than 12 months by disease category
- Patient receiving adjuvant endocrine therapy as their only form of therapy for early-stage breast cancer
- Solid tumor patients more than 6 months post treatment and their cancer is considered to be stable or in remission as determined by the Investigator
- AZD7442 administration at any time prior to day of enrollment
- Have a positive test for SARS-CoV-2 antigen performed by either Rapid Test or SARS-CoV-2 RNA by RT-PCR (Polymerase Chain Reaction) less than 90 days prior to enrollment
- Patient with a prior (within 90 days), current, or planned use of any of COVID-19 convalescent plasma, other monoclonal antibodies against SARS-CoV-2 or any other EUA approved SARS-CoV-2 treatment
- Patient with fever >100.0 F, and/or cough, chills, loss of smell or taste or shortness of breath or any other signs or symptoms consistent with COVID-19 within 5 days prior to enrollment
- Patient who has any known active acute respiratory infection
- Patient who has persistent (refractory to treatment for ≥ 14 days) bacterial or fungal infection
- Patient who has a past SARS-CoV-2 infection within 90 days prior to randomization
- Patient who has received vaccination with any dose of Janssen, Pfizer or Moderna COVID-19 vaccine less than 14 days prior to baseline for this study
- Planned use of any investigational, authorized, or approved vaccine for COVID-19 less than 14 days prior to administration of AZD7442 600 mg IM or IV
- Patient who is unwilling to have SARS-CoV-2 RBD-IgG antibody levels drawn at least 5 times
- Patient who is unwilling to receive treatment with IM or IV AZD7442
- Patient who is unwilling to complete baseline and up to 14 follow-up Experience/Clinical Outcome Assessment (COA) surveys.

	
 ➤ Patient who is unwilling to complete baseline and up to 5 follow-up QoL assessments ➤ Patient who is unwilling to have blood drawn for AZD7442 serum concentration at least 5 times ➤ Patient who is unwilling to have blood drawn twice for T-cell assay ➤ Patient whose native language is not English and does not have a person who can translate the regulatory documents, surveys and QoL assessments. ➤ Patient who is unable to provide Informed Consent or Authorization for Release of Health Information due to mental illness that requires a Legally Authorized Representative. ➤ Patient who is legally blind and does not have a witness/caregiver who has agreed to assist the patient in his/her participation in the study. ➤ Patient with a history of a severe allergic reaction (i.e., anaphylaxis) to any of the components of AZD7442 ➤ Patient with a history of severe allergic reaction (hypersensitivity) to any SARS-COV-2 vaccination, Polyethylene Glycol (PEG) or Polysorbate 80 ➤ Patient who is illiterate and does not have a witness/caregiver who has agreed to assist the patient in his/her participation in the study. ➤ Patient who is participating in an interventional trial for prophylaxis or treatment of SARS-CoV-2

9.0 Study Activities
	
9.1 Screening Activities
 
Total study enrollment will be based on approximately 80% of qualified enrolled subjects treated for solid tumors and approximately 20% of qualified enrolled subjects treated for hematologic malignancy.
 
 ➤ At the time of screening, all patients have (1) completed an FDA EUA or approved (Janssen, Moderna or Pfizer) COVID-19 single dose vaccine regimen, a two-dose vaccine regimen or one dose of a two-dose vaccine regimen; and/or (2) decided to receive or not receive an additional “booster” dose of Moderna, Pfizer or Janssen SARS-CoV-2 vaccine.

- In vaccinated patients, screening may occur at any time after 14 days post vaccination.
- Site personnel will draw blood for SARS-CoV-2 specific RBD-IgG antibody level at least 4 weeks or longer after completion of the most recent dose of any FDA approved SARS-CoV-2 vaccine.
- Blood drawn for SARS-CoV-2 RBD-IgG in all patients will be sent to LabCorp for analysis.
- Once blood is obtained for SARS-CoV-2 RBD-IgG, the patient may proceed to the Baseline Visit and be offered treatment with AZD7442. The SARS-CoV-2 specific RBD-IgG level is without charge to the patient.
- Site personnel will perform a nasal or buccal SARS-CoV-2 rapid antigen test in the office at the time of screening. If the SARS-CoV-2 rapid antigen test is negative, the patient may proceed to the baseline visit. If the SARS-CoV-2 rapid antigen test is positive, the patient will be referred for SARS-CoV-2 by RT-PCR test. If the RT-PCR test is positive, the patient is disqualified from study participation. If the SARS-CoV-2 by RT-PCR test is negative the patient may proceed to the baseline visit.
- Patients will digitally sign and site personnel will witness the Informed Consent Form (ICF)
- Site personnel will obtain CBC (including platelet count) if not performed within prior 30 days
- Patients will digitally sign Authorization for Release of Healthcare Records Form.

9.2 Baseline Activities

Baseline Activities are as follows:

- Patients will complete the baseline Experience/Clinical Outcome Assessment (COA) survey
- For Patients Receiving IM Dose Administration:

Site personnel will withdraw 1.5 mL of AZD8895 from each of two AZD8895 vials for a total of 3.0 ml into one syringe and in a separate syringe, withdraw 1.5 mL of

AZD1061 from each of two vials of AZD1061 for a total of 3.0 ml in one syringe and administer 3.0 ml of AZD8895 and 3.0 ml AZD1061 separately in sequential order IM into each thigh or gluteal muscle, with no participant receiving 3.0 ml of IM AZD8895 without also receiving the matching dose of 3.0 ml of IM AZD1061. One IM injection must be given in each thigh or gluteal muscle in sequence for a total of 600 mg (6.0 ml) administered.

➤ For Patients Receiving IV Dose Administration:

The criteria for IV administration of AZD7442 includes one or more of the following: platelet count $\leq 50,000$, coagulation deficiency, intravenous medication port in place, limited gluteal or thigh muscle mass.

The dose of AZD7442 for administration must be prepared using aseptic technique.

The total time from needle puncture of the vial to the start of administration must not exceed:

- 24 hours at 2 °C to 8 °C
- 4 hours at room temperature

AZD7442 is only stored refrigerated. The total time at room temperature prior to administration must not exceed 4 hours; otherwise, a new dose must be prepared using new vials. AZD7442 does not contain preservatives and any unused portion must be discarded.

Use a single 50 to 100 mL 0.9% sodium chloride or 5% dextrose for injection IV bag for both AZD8895 and AZD1061 infusion. Use a soft IV bag made of polyolefin (PO), polyvinylchloride (PVC), or polyethylene (PE).

Step 1:

For 600 mg dose of AZD7442, retrieve two vials each of AZD8895 and AZD1061.

Step 2:

Accurately withdraw 1.5 mL from each of the two vials of AZD8895 and transfer to the IV bag. Then, withdraw 1.5 mL from each of the two vials of AZD1061 and transfer to the same IV bag. Mix the bag by gently inverting to ensure homogeneity of the dose in the bag.

Step 3:

Administer the entire contents of the IV bag using IV administration sets containing low protein binding 0.2- μ m or 0.22- μ m filters made of polyethersulfone (PES). The target infusion time is 30 minutes and the target infusion rate is 20 mg/minute, which translates to IV pump programmable rates of approximately:

- 100 mL/hr for a 50 mL IV bag
- 200 mL/hr for a 100 mL IV bag

Step 4:

Flush the IV line according to local practices to ensure the full dose is administered. Infusion time does not include the final flush time. Flush the catheter with 0.9% sodium chloride for injection at the end of the infusion.

- Site personnel may administer AZD7442 600 mg IV ONLY under one of or more of the following conditions:
 - at the discretion of the Investigator if the patient would have less discomfort with an intravenous route (i.e., has significant weight loss and little gluteal or thigh muscle mass)
 - if the patient already has an indwelling medication “port” through which the patient receives intravenous drug administration.
 - if the patient’s platelet count $\leq 50,000/\mu$ l
 - if the patient has a history of a coagulation disorder
- AZD7442 may only be administered by IV infusion in settings in which healthcare providers have immediate access to medications to treat a severe infusion reaction, such as anaphylaxis, and the ability to activate the emergency medical system as necessary.
- Patients administered AZD7442 IV will be observed for immediate side effects and have vital signs measured every 15 minutes during the time of infusion and for the 60 minutes following the end of the infusion. All such vital signs will be record in the patient’s medical record.
- If an infusion-related reaction occurs, the AZD7442 infusion should be immediately terminated and appropriate medications including but not limited to diphenhydramine, other anti-histamines, methylprednisolone, epinephrine and/or other supportive care measures should be immediately provided.

- Patients will be observed for immediate side effects for 60 minutes following AZD7442 600 mg IM administration
- Site personnel will give all patients one SARS-CoV-2 Home Test Kit for at home testing of possible SARS-CoV-2 infection at the conclusion of the baseline visit
- Automatic request for patient medical records, pharmacy fill/refill data and medical insurance claims data for the 6 months prior to baseline will be sent and forwarded to MediMergent for analysis

9.3 Follow-Up Activities

Follow-Up activities are as follows:

- At Day 180 post-baseline, all patients will be administered a repeat dose of AZD7442 600 mg IM or IV. The window for this treatment will be +/- 5 days from the actual due date. The dose will be administered in the same manner as the baseline dose unless patient circumstances require a different route of administration. All requirements listed above for baseline AZD7442 administration both IV and IM will be followed for the repeat dose including the one-hour post-dose observation period.
- Patients will complete follow-up Patient Experience/COA surveys on days 2, 30, 60, 90, 120, 150, 180, 181, 210, 240, 270, 300, 330 and 360 post-baseline at home. The window for these surveys will be +/- 5 days from the actual survey due date except for day 2 survey which is +5 days only.
*NB - Study participants will complete all surveys via mobile phone, desktop, laptop, tablet computer or via Call Center. The study site is not responsible for patient completion of the surveys.
- Patients will complete QoL assessments on days 2, 30, 90, 180, 270, and 360 post-baseline at home. The window for these assessments will be +/- 5 days from the actual due date except for day 2 assessment which is + 5 days only.
- Site personnel will obtain blood for serum concentration of AZD7442 at days 30, 90, 180, 270 and 360 post-baseline in the office for all patients. The window for these blood draws will be +/- 5 days from the actual due date. All

serum concentration measurements will be sent to PPD Bioanalytical Laboratory in Richmond, VA for analysis.

- Site personnel will obtain blood for RBD-IgG antibody level at days 90, 180, 270 and 360 post-baseline in the office for all patients. The window for these blood draws will be +/- 5 days from the actual due date. All RBD-IgG antibody levels will be sent to LabCorp for analysis.
- Site personnel will obtain blood for T-cell assay at Day 30 post-baseline in the office for all patients and send to Isoplexis in Branford, CT for analysis. A subset of patients will be selected including 120 patients with hematologic malignancy and 60 patients with solid tumors in order to have site personnel obtain blood for repeat T-cell assay at Day 210 post-baseline in the office and send to Isoplexis in Branford, CT for analysis. The window for these blood draws will be +/- 5 days from the actual due date.
- In the event that a patient develops any symptoms that could be possibly related to SARS-CoV-2 infection at home or out of the office, the patient must immediately test themselves using the SARS-CoV-2 Home Test Kit that was given to them at enrollment or go to a facility that can perform an EUA approved Breath Test for SARS-CoV-2 infection.
- In the event a positive test from the SARS-CoV-2 Home Test Kit or EUA approved Breath Test for SARS-CoV-2 infection is recorded, the patient must go to a qualified testing center and receive a SARS-COV-2 RNA by RT-PCR nasal swab test. These include LabCorp or Quest Diagnostics or a location that uses one of these two labs for the analysis (e.g., CVS).
- A positive SARS-COV-2 RNA by RT-PCR test must be sent to a qualified genomics laboratory (LabCorp or Quest Diagnostics) for detailed virus analysis
- In the event that a patient tests positive for SARS-CoV-2 infection by SARS-COV-2 RNA by RT-PCR, the patient should be instructed to contact their oncology center immediately
- In the event that a patient tests positive for SARS COV-2 RNA by RT-PCR, the patient must have blood drawn for serum concentration of AZD7442, RBD-IgG antibody level and T-cell analysis in the office approximately 10

days after the patient reported a positive test or in whatever timeframe is the acceptable protocol for a positive patient returning safely to the office of the Investigator.

- In the event that a patient develops a SARS-CoV-2 infection with symptoms, the patient should be immediately treated in accordance with Investigator judgement. Such treatment should include the current standard of care for symptomatic SARS-CoV-2 positive infection depending upon availability of immediate treatment. Such patient will be followed until day 360 of the study with all study procedures and assessments.
- Automatic request for patient medical records, pharmacy fill/refill data and medical insurance claims data for all patients for the 12 months post-baseline will be sent and forwarded to MediMergent for analysis.

[figure not shown]
Schedule of Activities:

	Screening/ Day 1 Baseline	Day 2	Day 30	Day 60	Day 90	Day 120	Day 150	Day 180	Day 181	Day 210	Day 240	Day 270	Day 300	Day 330	Day 360
Visit Window (Days)		+5	± 5	± 5	± 5	± 5	± 5	± 5	± 5	± 5	± 5	± 5	± 5	± 5	± 5
Informed Consent	X														
Authorization for Release of Health Info	X														
Inclusion/ Exclusion	X														
CBC including Platelet Count (if necessary)	X														
SARS-CoV-2 antigen test by nasal swab	X														
SARS-CoV-2 RBD- IgG Antibody level	X				X			X				X			X
T-Cell Assay			X							X					
AZD7442 Administration	X							X							
Baseline Survey	X														
QoL Surveys		X	X		X			X				X			X

Follow-up Patient Experience/COA Surveys		X	X	X	X	X	X	X	X	X	X	X	X	X	X
Serum Concentration of AZD7442			X		X			X				X			X
SARS-CoV-2 by RT-PCR if home test positive and/or symptomatic		NOTE: In the event that a patient tests positive for SARS COV-2 by RT-PCR at any time, the patient must have blood drawn for serum concentration of AZD7442, RBD-IgG antibody level and T-cell analysis in the office approximately 10 days after the patient reported a positive test or in whatever timeframe is the acceptable protocol for a positive patient returning safely to the office of the Investigator.													

10.0 Immunologic Sub-Study Activities	
10.1 Sub-Study Secretome Assay
 
IsoPlexis’ Single Cell Multiplex Secretome Assay application measures T-cell polyfunctionality (i.e., the number of cells secreting multiple cytokines). From these data, the Polyfunctional Strength Index (PSI) will be calculated as a numeric output generated as the product of T-cell polyfunctionality multiplied by the intensity of the measured signal using fluorescent imaging. These data generate functional information relating to:
 
 • CD4 T-cells (Helper T-cells) which produce cytokines to activate immune cells including B-cells, CD-8 T-cells and macrophages. • CD8 T-cells (Cytotoxic T-cells) which destroy virus-infected cells and tumor cells by either lysis and/or apoptosis. 
10.2 CD4 and CD8 T-Cell Function
 
In general, CD4 and CD8 T-cell function increases during active SARS-CoV-2 infection reflecting stimulation and activation of T-cell immune response. The magnitude of this increase in T-cell function appears to be related to the severity of COVID-19 disease. Specifically, previous data acquired in immunocompetent subjects have reported that CD4 and CD8 T-cell function significantly increase in response to active SARS-CoV-2 infection in subjects with mild-to-moderate SARS-CoV-2 disease. However, subjects with moderate or more severe SARS-CoV-2 disease may have a blunted T-cell response due to “exhaustion” of the cells’ ability to mount a sustained cellular immune response.

The following table uses the Day 30 T-cell test as an example for guidance relating to the clinical interpretation of the T-cell test responses.

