- The trial met the primary endpoint, with a dose of 600mg of AZD7442 given by intramuscular (IM) injection reducing the risk of developing severe SARS-CoV-2 infection or death (from any cause) by 50% compared to placebo in outpatients who had been symptomatic for seven days or less. The trial recorded 18 events in the AZD7442 arm (18/407) and 37 in the placebo arm (37/415). The LAAB was well tolerated in the trial.
- In a prespecified analysis of participants who received treatment within five days of symptom onset, AZD7442 reduced the risk of developing severe SARS-CoV-2 infection or death (from any cause) by 67% compared to placebo, with nine events in the AZD7442 arm (9/253) and 27 in the placebo arm (27/251).
- AstraZeneca has submitted a request to the US Food and Drug Administration (FDA) for Emergency Use Authorization (EUA) for AZD7442, its long-acting antibody (LAAB) combination, for prophylaxis of symptomatic SARS-CoV-2 infection. The EUA request filing includes safety and efficacy data from the **PROVENT** and **STORM CHASER** Phase III trials and the Phase I trial. AZD7442 was optimized using

AstraZeneca's proprietary YTE half-life extension technology which more than triples the durability of its action compared to conventional antibodies.

- Preliminary 'in vitro' findings demonstrate that AZD7442 has broad anti-COVID activity, and in particular neutralizes recent emergent SARS-CoV-2 viral variants, including Delta and Mu variants.
- In June 2021, AstraZeneca announced results from the STORM CHASER trial assessing the safety and efficacy of AZD7442, a long-acting antibody (LAAB) combination, for the prevention of symptomatic SARS-CoV-2 infection in participants recently exposed to the SARS-CoV-2 virus. The trial did not meet the primary endpoint of post-exposure prevention of symptomatic SARS-CoV-2 infection with AZD7442 compared to placebo.
- Trial participants were unvaccinated adults 18 years and over with confirmed exposure to a person with a case of the SARS-CoV-2 virus within the past eight days. In the overall trial population, AZD7442 reduced the risk of developing symptomatic COVID-19 by 33% (95% confidence interval (CI): -26, 65) compared to placebo, which was not statistically significant.

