- On December 8, 2021, AZD7442 (Evusheld) received initial emergency use authorization (EUA) in the US for the pre-exposure prophylaxis (prevention) of SARS-CoV-2 infection. The Food and Drug Administration (FDA) granted the EUA for AZD7442 for pre-exposure prophylaxis of SARS-CoV-2 infection in adults and adolescents (aged 12 and older who weigh 40kg or more) with moderate to severe immune compromise due to a medical condition or immunosuppressive medications and who may not mount an adequate immune response to SARS-CoV-2 vaccination, as well as those individuals for whom SARS-CoV-2 vaccination is not recommended. Recipients should not be currently infected with or had recent known exposure to a person infected with SARS-CoV-2. As a result of the prevalence of the omicron variants BA.1 and BA.1.1, the EUA was revised and updated on February 24, 2022 to increase the dose of AZD7442 (Evusheld) from 300 mg IM to 600 mg IM.
- AZD7442 is the only antibody therapy authorized in the US for SARS-CoV-2 pre-exposure prophylaxis and the only SARS-CoV-2 antibody delivered as an intramuscular dose (300 mg tixagevimab and 300 mg cilgavimab). About seven million people in the US are immunocompromised and may benefit from AZD7442 for pre-exposure prophylaxis of SARS-CoV-2 infection. This includes people with blood cancers or other cancers being treated with chemotherapy, and those taking medications after an organ transplant or who are taking immunosuppressive drugs for conditions including multiple sclerosis and rheumatoid arthritis.

- The primary data supporting the AZD7442 EUA are from the ongoing PROVENT Phase III pre-exposure prevention trial, which showed a statistically significant reduction (77% at primary analysis, 83% at median six-month analysis) in the risk of developing symptomatic SARS-CoV-2 infection compared to placebo, with protection from the virus continuing for at least six months. Data from the Phase III STORM CHASER post-exposure trial and the AZD7442 Phase I trial also supported the EUA.

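### Section 9.3 orders the Day 180 repeat dose for every patient with no mandatory withhold criterion and no scheduled pre-dose review; the only patient-level relief is discretion after an adverse event

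*Protocol*

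**What the plan says.** Section 9.3 sets the rule for the second dose: "At Day 180 post-baseline, all patients will be administered a repeat dose of AZD7442 600 mg IM or IV", within a window of 5 days either side. The only patient-level variation is a change of route. The section then adds that "All requirements listed above for baseline AZD7442 administration both IV and IM will be followed for the repeat dose", including the one-hour observation. The requirements it points back to, in 9.2, concern preparation, route, infusion setting and observation.

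The Schedule of Activities marks dosing at Day 1 and Day 180. It marks Inclusion/Exclusion, the blood count and the row "SARS-CoV-2 antigen test by nasal swab" at Screening/Day 1 only.

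At entry, 8.2 excludes "Patient with a history of a severe allergic reaction (i.e., anaphylaxis) to any of the components of AZD7442" and "Women who are pregnant, breast feeding or of child bearing potential and not using contraception", as well as patients with a recent positive test. Section 23.5, describing the emergency authorization, recites that "Recipients should not be currently infected with or had recent known exposure to a person infected with SARS-CoV-2".

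For a patient who develops symptomatic infection during the study, 9.3 says: "Such patient will be followed until day 360 of the study with all study procedures and assessments".

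**The concern.** Dose 1 is the exposure that can reveal an allergy to the product, and six months is long enough for a pregnancy to begin. The protocol treats both states as reasons not to give the drug at entry. At Day 180 it gives a universal instruction and no occasion to check for either. Up to 75 sites would each have to decide alone whether a patient who reacted severely to dose 1, or who is now pregnant, should be dosed again.

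The main stake is patient safety in a small group. A second stake is data. If the only way to avoid dose 2 is to withdraw the patient, the Day 270 and Day 360 concentrations and the later safety follow-up are lost as well.

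**Working it through.** The plan gives no figure to reproduce, so the check sets the clauses side by side for each state that could arise between doses.

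| State at Day 180 | At entry | What happens after dose 1 | Is withholding dose 2 required? |
|---|---|---|---|
| Severe hypersensitivity or infusion reaction to dose 1 | Severe allergy excluded (8.2) | 9.2: stop that infusion and treat. 25.16: local monitoring guidelines, pre-medication allowed. 25.18/25.19: investigator may withdraw the patient or deviate | No; discretion only |
| Pregnancy | Excluded (8.2) | 8.1: contraception for the 12 months. 25.20: report and follow the outcome; pregnancy is not itself an adverse event | No; the adverse-event discretion does not clearly apply |
| Current infection | Recent positive test excluded (8.2) | 9.3: self-test on symptoms, RT-PCR, contact the center; stay on study procedures. 25.7.2: positive PCR and symptoms are adverse events, so 25.18/25.19 can apply | No; discretion only |

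Other clauses that might fill the gap:

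1. Section 12.1 ties administration to FDA guidelines for the IM route only and names no stop condition. For the IV route it points back to 9.2.
2. The redosing remit in 21.1 is a study-level recommendation attached to the interim analysis. It is not a patient-level check.
3. The post-baseline RT-PCR row in the Schedule depends on a positive home test or symptoms. It is not tied to dosing, and no rule links its result to dose 2.

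**Number of patients.** The protocol gives no reaction, infection or pregnancy rate. Section 1.1 mentions only isolated cases of anaphylaxis with the antibody class. Purely as illustration, with N = 1,500:

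- Severe dose-1 reaction at an assumed 0.1% to 0.5%: 1,500 × 0.001 = 1.5, to 1,500 × 0.005 = 7.5 patients.
- Infected when dose 2 falls due = N × annual incidence × days infected / 365. At an assumed 5% and 5 days: 1,500 × 0.05 × 5/365 = 1.0. At an assumed 20% and 14 days: 1,500 × 0.20 × 14/365 = 11.5.
- Pregnancy cannot be sized and is expected to be rare.

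**Primary endpoint.** Suppose a fraction p of patients has no second dose and their geometric mean concentration is r times that of redosed patients. The overall mean log concentration at Day 270 or Day 360 then moves by p × ln r. At p = 0.005 this is 0.5% of the log difference between the two groups, whatever r is. The 17.6 model also includes overall dose.

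**The case against.** The strongest defence is that the investigator already has patient-level authority. Section 25.18 allows withdrawal after any adverse event at any time, and 25.19 leaves continuation to the investigator after an adverse event or emergency. Section 25.7.2 counts events in the first 24 hours after dosing, SARS-CoV-2 symptoms and a positive PCR as adverse events. A reader might infer from 9.3 that a severe reaction or an infection cannot stop dose 2. These clauses show that this is too strong. What they do not supply is a mandatory criterion, a scheduled check, or a way to omit the dose while keeping the patient in the study.

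The allergy exclusion in 8.2 has no time limit, so a patient with anaphylaxis after dose 1 could be said to meet it from then on. That reading is possible, but eligibility is scheduled for review at Day 1 only, and the remedy it implies is again leaving the study.

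For pregnancy, 8.1 requires contraception throughout and 25.20 requires a report within 24 hours. Both make an unnoticed pregnancy less likely. Neither says what the report means for dose 2.

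For infection, the self-testing and RT-PCR steps, and the provision in 9.3 that a positive patient returns for the infection blood draw at about 10 days or when it is safe, make routine dosing of a known infectious patient unlikely. A reader might take the sentence keeping infected patients on all procedures as an order to dose them. It is mainly a retention sentence and simply makes no exception for dose 2. Nor does the protocol show that dosing in infection is harmful: of 600 mg IM in symptomatic outpatients, 23.5 reports "The LAAB was well tolerated in the trial".

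A reader might also add the illustrative ranges to get about 3 to 19 patients (2.5 to 19.0, or 0.2% to 1.3% of 1,500). That total is not supportable. Every rate is assumed, 11.5 of the upper 19.0 (61%) comes from the infection group, where no harm is shown, and the infection figure ignores both the return-when-safe provision and the dosing window.

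**Conclusion.** The gap is real but narrow. Section 9.3 fixes a universal second dose with no mandatory withhold criterion and no scheduled pre-dose review, and the relief elsewhere is permissive and tied to adverse events. It matters mainly for a severe dose-1 hypersensitivity or infusion reaction, where only discretion applies, and for pregnancy, which that discretion does not clearly cover. For current infection the point is limited to consistency with the authorization condition recited in 23.5.

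This is a missing redosing condition. A reader might call it a contradiction between 8.2 and 9.3, but the 8.2 items are entry criteria, so the text does not support that.

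Few patients are affected, and their number cannot be established from the protocol. The effect on the primary endpoint is small. The point is worth correcting because the possible harm to an individual is serious and the correction is cheap, but it ranks low among changes to the plan.

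**What to change.** 1. In 9.3, limit the repeat dose to patients other than those who had a severe hypersensitivity or infusion reaction to dose 1 and those who are pregnant. For confirmed current infection, have the sponsor specify whether the dose is deferred until recovery or omitted.
2. Define current infection by a positive test, not by symptoms alone. The qualifying symptoms in 14.1 include fatigue, nausea, diarrhea and cough, which plausibly occur in patients on cancer therapy without infection. A symptom bar could withhold prophylaxis from many more patients than intended.
3. Make the 9.3 sentence on continuing study procedures in infected patients subject to this condition.
4. Add one pre-dose review row to the Schedule at Day 180: dose-1 reaction history, known infection status and pregnancy status.
5. State that patients not redosed remain in follow-up to Day 360, and record the doses each patient actually received so that the 17.6 model and any summary can identify them.

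The cost is a few sentences and one Schedule row at a visit already planned for dosing and blood draws; no new laboratory test is needed. A few patients would miss dose 2 and so fall outside the per-protocol set, because 17.4 requires all administrations. They remain eligible for the ITT set, which does not require the second dose.
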